Hypophysitis	Grade 2	Withhold	
 
Administer corticosteroids and initiate hormonal replacements as clinically indicated.
 
	
 
Monitor for signs and symptoms of hypophysitis (including hypopituitarism and adrenal insufficiency)
 

	Grade 3 or 4	Withhold or permanently discontinue 		
Hyperthyroidism	Grade 2	Continue	
 
Treat with non-selective beta-blockers (eg, propranolol) or thionamides as appropriate
 
	
 
Monitor for signs and symptoms of thyroid disorders.
 

	Grade 3 or 4	Withhold or permanently discontinue 		
Hypothyroidism	Grade 2-4	Continue	
 
Initiate thyroid replacement hormones (eg, levothyroxine or liothyronine) per standard of care
 
	
 
Monitor for signs and symptoms of thyroid disorders.
 

Nephritis and Renal dysfunction	Grade 2	Withhold	
 
Administer corticosteroids (prednisone 1-2 mg/kg or equivalent) followed by taper.
 
	
 
Monitor changes of renal function
 

	Grade 3 or 4	Permanently discontinue		
Myocarditis	Grade 1 or 2	Withhold	
 
Based on severity of AE administer corticosteroids
 
	
 
Ensure adequate evaluation to confirm etiology and/or exclude other causes
 

	Grade 3 or 4	Permanently discontinue		
All other immune-related AEs	Intolerable/persistent Grade 2	Withhold	
 
Based on type and severity of AE administer corticosteroids
 
	
 
Ensure adequate evaluation to confirm etiology and/or exclude other causes
 

	Grade 3	Withhold or discontinue based on the type of event. Events that require discontinuation include and not limited to: Guillain-Barre Syndrome, encephalitis		

9458- Protocol Version Date 28 Feb 2019

	Grade 4 or recurrent Grade 3	Permanently discontinue		

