### **5.5.1 Acceptable Concomitant Medications**

All treatments that the investigator considers necessary for a subject's welfare may be administered at the discretion of the investigator in keeping with the community standards of medical care. All concomitant medication will be recorded on the case report form (CRF) including all prescription, over-the-counter (OTC), herbal supplements, and IV medications and fluids. If changes occur during the trial period, documentation of drug dosage, frequency, route, and date may also be included on the CRF.

All concomitant medications received within 28 days before the first dose of trial treatment and 30 days after the last dose of trial treatment should be recorded. Concomitant medications administered after 30 days after the last dose of trial treatment should be recorded for SAEs and events of clinical interest (ECIs) as defined in Section 7.2.

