### **5.5.2 Prohibited Concomitant Medications**

Subjects are prohibited from receiving the following therapies during the Screening and Treatment Phase (including retreatment for post-complete response relapse) of this trial:

- Antineoplastic systemic chemotherapy or biological therapy
- Immunotherapy not specified in this protocol
- Chemotherapy not specified in this protocol
- Investigational agents other than pembrolizumab
- Radiation therapy
- Live vaccines within 30 days prior to the first dose of trial treatment and while participating in the trial. Examples of live vaccines include, but are not limited to, the following: measles, mumps, rubella, varicella/zoster, yellow fever, rabies, BCG, and typhoid vaccine.
- Systemic glucocorticoids for any purpose other than to modulate symptoms from an event of clinical interest of suspected immunologic etiology. The use of physiologic doses of corticosteroids may be approved after consultation with the PI.

Subjects who enroll in the context of persistent MRD following prior treatment will not be allowed to continue this prior treatment. Subjects who, in the assessment by the investigator, require the use of any of the aforementioned treatments for clinical management should be

9458- Protocol Version Date 28 Feb 2019

removed from the trial. Subjects may receive other medications that the investigator deems to be medically necessary.

The Exclusion Criteria describes other medications which are prohibited in this trial.

There are no prohibited therapies during the Post-Treatment Follow-up Phase.

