## **5.6 Rescue Medications & Supportive Care**

### **5.6.1 Supportive Care Guidelines**

Subjects should receive appropriate supportive care measures as deemed necessary by the treating investigator. Suggested supportive care measures for the management of adverse events with potential immunologic etiology are outlined below. Where appropriate, these guidelines include the use of oral or intravenous treatment with corticosteroids as well as additional anti-inflammatory agents if symptoms do not improve with administration of corticosteroids. Note that several courses of steroid tapering may be necessary as symptoms may worsen when the steroid dose is decreased. For each disorder, attempts should be made to rule out other causes such as relapsed disease or bacterial or viral infection, which might require additional supportive care. The treatment guidelines are intended to be applied when the investigator determines the events to be related to pembrolizumab.

Note: if after the evaluation the event is determined not to be related, the investigator is instructed to follow the ECI reporting policies but does not need to follow the treatment guidance. Refer to Section 5.2.1 for dose modification.

It may be necessary to perform conditional procedures such as bronchoscopy, endoscopy, or skin photography as part of evaluation of the event.

- **Pneumonitis:**

- For **Grade 2 events**, treat with systemic corticosteroids. When symptoms improve to Grade 1 or less, steroid taper should be started and continued over no less than 4 weeks.
- For **Grade 3-4 events**, immediately treat with intravenous steroids. Administer additional anti-inflammatory measures, as needed.
- Add prophylactic antibiotics for opportunistic infections in the case of prolonged steroid administration.

- **Diarrhea/Colitis:**

Subjects should be carefully monitored for signs and symptoms of enterocolitis (such as diarrhea, abdominal pain, blood or mucus in stool, with or without fever) and of bowel perforation (such as peritoneal signs and ileus).

- All subjects who experience diarrhea/colitis should be advised to drink liberal quantities of clear fluids. If sufficient oral fluid intake is not feasible, fluid and electrolytes should be substituted via IV infusion. For Grade 2 or higher diarrhea, consider GI consultation and endoscopy to confirm or rule out colitis.

9458- Protocol Version Date 28 Feb 2019

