  - For **Grade 2** events, monitor liver function tests more frequently until returned to baseline values (consider weekly).
    - Treat with IV or oral corticosteroids
  - For **Grade 3-4** events, treat with intravenous corticosteroids for 24 to 48 hours.
  - When symptoms improve to Grade 1 or less, a steroid taper should be started and continued over no less than 4 weeks.
  
- **Renal Failure or Nephritis:**
  - For **Grade 2** events, treat with corticosteroids.
  - For **Grade 3-4** events, treat with systemic corticosteroids.
  - When symptoms improve to Grade 1 or less, steroid taper should be started and continued over no less than 4 weeks.
  
- **Management of Complications Unique to HCT or Cellular Immunotherapy:** A potential risk of administering pembrolizumab to patients who have previously received HCT or other cellular immunotherapy modalities like CAR-T cells is a recrudescence of toxicities that are germane to these specific therapies, including GVHD, cytokine release syndrome (CRS), and neurologic toxicity. The manifestations of such events (e.g., diarrhea, pneumonitis, rash, hepatitis, etc.) are included in the specific guidelines above. As needed and on a case-by-case basis, best local practices and additional expert consultation can also be instituted as needed for management of these toxicities, should they develop. Recording and reporting of these adverse events will follow the same guidelines as those set out elsewhere in the protocol (Section 7.2).
  
- **Management of Infusion Reactions:** Signs and symptoms usually develop during or shortly after drug infusion and generally resolve completely within 24 hours of completion of infusion.

Minor deviations from these guidelines will be permitted, at the discretion of the treating investigator.

Table 4 below shows treatment guidelines for subjects who experience an infusion reaction associated with administration of pembrolizumab (MK-3475). Minor deviations from these guidelines will be permitted, at the discretion of the treating investigator.

Table 4 Infusion Reaction Treatment Guidelines

NCI CTCAE Grade	Treatment	Premedication at subsequent dosing
Grade 1 Mild reaction; infusion interruption not indicated; intervention not indicated	Increase monitoring of vital signs as medically indicated until the subject is deemed medically stable in the opinion of the investigator.	None

9458- Protocol Version Date 28 Feb 2019

NCI CTCAE Grade	Treatment	Premedication at subsequent dosing

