## **7.1.2 Clinical Procedures/Assessments**

### **7.1.2.1 Adverse Event (AE) Monitoring**

The investigator or qualified designee will assess each subject to evaluate for potential new or worsening AEs as specified in the Trial Flow Chart and more frequently if clinically indicated. Adverse experiences will be graded and recorded throughout the study and during the follow-up period according to the most current available version of the NCI CTCAE (see Section 12.2). Toxicities will be characterized in terms regarding seriousness, causality, toxicity grading, and action taken with regard to trial treatment.

Please refer to section 7.2 for detailed information regarding the assessment and recording of AEs.

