## **7.2 Assessing and Recording Adverse Events**

An adverse event is defined as any untoward medical occurrence in a patient or clinical investigation subject administered a pharmaceutical product and which does not necessarily have to have a causal relationship with this treatment. An adverse event can therefore be any unfavorable and unintended sign (including an abnormal laboratory finding, for example), symptom, or disease temporally associated with the use of a medicinal product or protocol-specified procedure, whether or not considered related to the medicinal product or protocol-specified procedure. Any worsening (i.e., any clinically significant adverse change in

9458- Protocol Version Date 28 Feb 2019

frequency and/or intensity) of a preexisting condition that is temporally associated with the use of Merck's product is also an adverse event.

Changes resulting from normal growth and development that do not vary significantly in frequency or severity from expected levels are not to be considered adverse events. Examples of this may include, but are not limited to, menopause occurring at a physiologically appropriate time.

Merck product includes any pharmaceutical product, biological product, device, diagnostic agent or protocol-specified procedure, whether investigational (including placebo or active comparator medication) or marketed, manufactured by, licensed by, provided by or distributed by Merck for human use.

Adverse events may occur during the course of the use of Merck product in clinical trials or within the follow-up period specified by the protocol, or prescribed in clinical practice, from overdose (whether accidental or intentional), from abuse and from withdrawal.

Adverse events may also occur in screened subjects during any pre-allocation baseline period as a result of a protocol-specified intervention, including washout or discontinuation of usual therapy, diet, placebo treatment or a procedure.

Relapse/progression of ALL is not considered an adverse event unless it is considered to be drug related by the investigator.

All ECIs (as defined in Section 7.2.3.2) and other grade 3 or higher adverse events will be recorded from the time the consent form is signed through 30 days following cessation of treatment and at each examination on the Adverse Event case report forms/worksheets. The reporting timeframe for adverse events meeting any serious criteria is described in section 7.2.3.1.

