### **7.2.3.2 Events of Clinical Interest**

Selected non-serious and serious adverse events are also known as Events of Clinical Interest (ECI) and must be reported within 2 working days to Merck Global Safety. (Attn: Worldwide Product Safety; [contact]).

For the time period beginning when the consent form is signed until treatment allocation/randomization, any ECI, or follow up to an ECI, that occurs to any participant must be reported within 2 working days to Merck Global Safety if it causes the participant to be excluded from the trial, or is the result of a protocol-specified intervention, including but not limited to washout or discontinuation of usual therapy, diet, placebo treatment or a procedure.

For the time period beginning at treatment allocation/randomization through 90 days following cessation of treatment, or 30 days following cessation of treatment if the participant initiates new anticancer therapy, whichever is earlier, any ECI, or follow up to an ECI, whether or not related to Merck product, must be reported within 2 working days to Merck Global Safety.

9458- Protocol Version Date 28 Feb 2019

1. an overdose of Merck product, as defined in Section 7.2.1 - Definition of an Overdose for This Protocol and Reporting of Overdose to the Sponsor-Investigator, that is not associated with clinical symptoms or abnormal laboratory results.
2. an elevated AST or ALT lab value that is greater than or equal to 3X the upper limit of normal and an elevated total bilirubin lab value that is greater than or equal to 2X the upper limit of normal and, at the same time, an alkaline phosphatase lab value that is less than 2X the upper limit of normal, as determined by way of protocol-specified laboratory testing or unscheduled laboratory testing.\*

\*Note: These criteria are based upon available regulatory guidance documents. The purpose of the criteria is to specify a threshold of abnormal hepatic tests that may require an additional evaluation for an underlying etiology. The trial site guidance for assessment and follow up of these criteria can be found in the Investigator Trial File Binder (or equivalent).

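### Section 7.2 is not consistent on whether a non-serious grade 1-2 flare of GVHD, CRS or neurologic toxicity after prior transplant or cellular therapy must be entered as an adverse event

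*Combined protocol and SAP*

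**What the plan says.** Exclusion criteria 11 and 12 (Section 5.1.3) let in subjects with a prior allogeneic transplant or prior cellular immunotherapy, subject to conditions. These include no active GVHD, and resolution of any CRS or neurologic toxicity from the cell product.

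Section 5.6.1 states that pembrolizumab may bring GVHD, CRS or neurologic toxicity back in such subjects. It manages their manifestations under the organ-specific guidelines and adds: "Recording and reporting of these adverse events will follow the same guidelines as those set out elsewhere in the protocol (Section 7.2".

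The recording provisions are these:

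- Section 7.2, opening rule: "All ECIs (as defined in Section 7.2.3.2) and other grade 3 or higher adverse events will be recorded", from consent to 30 days after treatment stops.
- Section 7.2.3.2: "Selected non-serious and serious adverse events are also known as Events of Clinical Interest (ECI". Two items follow: an overdose without symptoms or abnormal laboratory results, and a combined AST/ALT, bilirubin and alkaline phosphatase pattern.
- Section 7.2.3.1: serious events are reported at any grade.
- Section 7.2.4 and Table 6: changes of CTCAE grade within an episode are entered on the AE form. A physician evaluates all AEs, and the relationship assessment goes on the case report form.
- Section 7.1.2.1: "Adverse experiences will be graded and recorded throughout the study and during the follow-up period", with no grade floor, followed by a pointer to Section 7.2 for the detail.

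Two other sections use the ECI term more broadly. Section 5.5.2 allows steroids for an "event of clinical interest of suspected immunologic etiology". Section 5.6.1 says that, if a suspected immune event proves unrelated to drug, "the investigator is instructed to follow the ECI reporting policies".

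**The concern.** The protocol identifies a specific hazard in a specific group and then sends its recording to rules that may not require an entry below grade 3. The low-grade events are not trivial for treatment. Table 3 withholds pembrolizumab and gives steroids for grade 2 pneumonitis, grade 2 diarrhea/colitis and grade 2 liver abnormalities. It also withholds for other immune-related events that are "Intolerable/persistent Grade 2". Recurrent grade 2 pneumonitis ends treatment, as does an AE that has not resolved within 12 weeks of the last dose.

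Secondary objective 1 (Section 3.2) is to describe the toxicity profile in previously treated ALL. If the entry rule is read narrowly, a flare that interrupted or ended dosing could be absent from that description. If staff read the rules differently, the count depends on the reading.

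**Working it through.** No sample-size, power or error-rate figure is involved, so the check applies each recording rule to each kind of flare.

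**Step 1: match by name.** Section 5.6.1 names three toxicities (GVHD, CRS, neurologic). Section 7.2.3.2 lists two ECIs. None of the three is named there, and neither item is a general immune-related category. The ECI usage in Sections 5.5.2 and 5.6.1 therefore has no matching definition.

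**Step 2: match by content.** A liver flare can still qualify. The ECI pattern needs AST or ALT at least 3 x ULN, total bilirubin at least 2 x ULN, and alkaline phosphatase below 2 x ULN. Assume a bilirubin ULN of 1.0 to 1.4 mg/dL, which the documents do not give. Then 2 x ULN = 2.0 to 2.8 mg/dL, inside liver stage +1 of Section 12.4 (2.0 to 2.9 mg/100 ml), which is overall GVHD Grade II. A low-grade liver flare can thus be an ECI if the enzyme conditions also hold.

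**Step 3: apply the rules.**

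| Flare after prior HCT or cellular therapy | Opening rule of 7.2, with 7.2.3 | 7.2.4 and Table 6, read literally |
|---|---|---|
| Serious, any grade | Captured (7.2.3.1) | Captured |
| Non-serious, grade 3 or higher | Entry required | Entry required |
| Grade 1-2 liver flare meeting the laboratory pattern | Entry required, as an ECI | Not needed |
| Grade 2, drug held, falls to grade 0-1, drug resumed | Not required | Required: the grade changed |
| Grade 2, drug held, does not improve | Not required | No grade change; only the relationship sentence could require it |
| Grade 1-2 at one grade, no hold | Not required | No grade change; only the relationship sentence could require it |

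The fourth row rests on Section 5.2.1.2, where drug resumes only once the AE is at grade 1 or 0. The two columns disagree there. In the last two rows, entry depends wholly on how widely the relationship sentence is read.

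**Step 4: look for another route.**

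- Section 7.1.5.3.1 follows AEs above grade 1 to resolution. That is a follow-up rule, not an entry rule.
- Table 6 lets the investigator class an important medical event as serious, at discretion.
- Section 7.1.5.3.2 notes grade 3 or higher acute GVHD, but only after a transplant given following study treatment.
- Section 5.5.1 says "All concomitant medication will be recorded on the case report form (CRF", and the data-management text under Section 11.5 requires copies of medical records. A flare could be partly reconstructed from these, but no such review is planned.

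**Step 5: grading scale.** Section 7.2.4 uses CTCAE for all AEs. Section 12.4 has a separate acute GVHD scale, on which a +3 skin rash can be overall Grade II. Section 5.6.1 does not say which scale decides whether a GVHD flare reaches grade 3.

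**Step 6: what a subset table could show.** The documents do not give the number of prior-HCT or prior-cellular-therapy subjects, so assume N = 3 to 10. For one event in N, the exact 95% lower limit is 1 - 0.975^(1/N). The upper limit solves (1-p)^N + N p (1-p)^(N-1) = 0.025.

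- N = 3: 0.8% to 90.6%
- N = 5: 0.5% to 71.6%
- N = 10: 0.3% to 44.5%

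These widths show that a subset table can only describe. They do not measure the recording gap.

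**The case against.** The strongest reply is that Section 7.2 already covers most of what matters. The grade-change sentence in Section 7.2.4 literally captures a flare that is held at grade 2 and resumed at grade 0-1. Table 6 also puts the relationship assessment on the case report form for AEs the physician evaluates. This stands in part. It makes many held-and-resumed flares arguably recordable. It does not settle the matter, because both sentences can also be read as applying only to AEs that the opening rule already makes recordable. Nor does the grade-change sentence reach a flare that stays at one grade.

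Second, a grade 3 floor is a legitimate choice. Section 7.1.5.3.2 uses the same threshold for later GVHD, and no section promises an any-grade count. That also stands: the documents do not oblige the sponsor to collect lower grades. The case for doing so here is that the protocol singled out this risk and its rules do not agree.

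Third, the scope could look arbitrary, since non-serious grade 2 pneumonitis or colitis falls under the same opening rule. That is fair, and the fix allows for it.

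A reader might infer that every non-serious grade 1-2 flare escapes entry. The liver pattern and Section 7.2.4 show otherwise. A reader might also infer that Section 7.1.2.1 sets a rival any-grade rule. It does not, because it refers to Section 7.2 for the detail.

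**Conclusion.** The point holds as an inconsistency within Section 7.2, together with undefined use of the ECI term in Sections 5.5.2 and 5.6.1. A non-serious low-grade flare can go unrecorded, most clearly one with no grade change. A grade 2 flare that holds drug can also be missed if the opening rule is taken to govern. Voluntary entry is not forbidden; what is missing is a clear requirement.

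The number of events affected cannot be computed, because neither the subset sizes nor a flare rate is given. It would go too far to infer that safety-critical events are lost, since serious and grade 3 or higher flares are captured. The primary endpoint, the two-stage rule and the early-relapse stopping rule are untouched. What is at stake is the completeness of a descriptive secondary objective, so this is a low-cost improvement to consider. The conclusion rests on the text alone; the assumed bilirubin ULN and subset sizes serve only as illustration.

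**What to change.** 1. In Sections 7.2 and 5.6.1, require AE-form entry at any grade, in subjects with prior allogeneic HCT or cellular therapy, of GVHD (acute GVHD graded by Section 12.4), CRS, and neurologic toxicity judged a possible recrudescence. That last qualifier keeps out stable neuropathy of up to grade 2, which exclusion criterion 6 allows at entry. The window runs from first dose to 30 days after treatment stops, or to a new HCT or cell therapy if earlier. Do not make these events ECIs; expedited reporting to the drug supplier is not needed.
2. Preferably, also require entry of any grade 2 immune-related AE that leads to a dose hold, steroids or discontinuation, so that grade 2 pneumonitis or colitis is treated alike.
3. State how the opening rule of Section 7.2 and the grade-change sentence of Section 7.2.4 fit together. In Sections 5.5.2 and 5.6.1, replace ECI with immune-related AE wherever the Section 7.2.3.2 list is not meant. Section 7.1.2.1 needs no new cross-reference.
4. Report these events as descriptive n/N: GVHD among prior-HCT subjects, CRS and neurologic toxicity among prior-cellular-therapy subjects. Prior treatments are already reviewed (Section 7.1.1.5.2), so N needs no new data.

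The cost is a few sentences, a few case report form entries and two or three table lines. AE review is already scheduled each cycle (Section 6.1). The drawbacks are reliance on investigator judgement for possible recrudescence and wide intervals in small subsets.
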